## **4. Statistical Analyses**

This section provides a detailed description of the statistical analyses and methods, tables, listings, and figures. SAP Table shells are presented in Section 5.1.

The definitions of the analysis populations are listed. The general description of the planned analysis is provided. Descriptive and baseline characteristics will be generated for the purpose of describing the study population. Because the sample size is small, sometimes the most informative way of presenting the data will be through graphs or listing of the raw data.

The primary and secondary efficacy endpoints will be analyzed using the intent-to-treat (ITT) and per protocol populations. The least squares mean and two-sided 95% confidence interval (CI) for the between-treatment differences will be estimated from the models. The Hodges-Lehmann analysis of median differences will be produced for some of the secondary efficacy endpoints. Relative risk (RR) or odds ratio (OR) with 95% CI will be presented for some of the binary endpoints. Longitudinal models will be used to analyze some of the efficacy endpoints. These models will focus on the difference between baseline and end of the double-blind treatment as well as end of

the open-label treatment; measurements taken before the end of the double-blinded treatment will be used to increase the precision of the estimates of the changes from baseline to the both end of the double-blind treatment and the end of the open-label treatment. Sensitivity analyses will be performed to examine the potential outliers and influential points. These measurements will be assessed by visual examination of histograms and normal probability plots of residuals from the models. The methods or statistical tests that will be used in the primary and secondary efficacy analyses and safety analyses are described. Details are provided below.

#### 4.1 Analysis populations

The analysis populations are:

- **Safety population:** The safety population is comprised of all subjects who are randomized and received at least one dose of study treatment and all subjects in the control group who did not withdraw or were not withdrawn. This population will be used to assess comparative safety information.
- **Intent-to-treat population:** The intent-to-treat (ITT) population (full analysis set) is comprised of all subjects who are randomized. Subjects in the ITT population will be categorized by their randomized treatment assignment. This population will be used to assess comparative efficacy information.
- **Per protocol population:** The per protocol (PP) population includes all subjects in the ITT population who do not have pre-defined major deviations from the protocol that may affect the primary (and secondary) endpoints (i.e., subjects who have not gone through the third upper endoscopy and biopsy at the end of the double-blind treatment, subjects with a compliance below 80%, etc.). The PP population will be used to perform confirmatory analyses of the primary efficacy evaluation.

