2. SYNOPSIS

NAME OF SPONSOR: [name]	PROTOCOL No.: SMILEE
NAME OF STUDY TREATMENT: Viaskin® Milk (DBV: Allergen extract of milk in Viaskin® epicutaneous delivery system)	
TITLE OF STUDY: A double-blind, placebo-controlled, randomized trial to Study efficacy and safety of the Viaskin® Milk for Treating milk induced Eosinophilic Esophagitis in children	
STUDY CENTERS: This is a single site study conducted in United States. The only site will be The Children's Hospital of Philadelphia.	
STUDY PERIOD: Recruitment will stop when approximately 22 subjects have been randomized in the study. Subject's participation in the study will last approximately 2 years	PHASE OF DEVELOPMENT: Phase IIA
PLANNED STUDY DURATION: approximately 3 years.	
OBJECTIVES: The objectives of this study are: 
 • To assess the efficacy of Viaskin® Milk epicutaneous immunotherapy (EPIT) in subjects with milk-induced eosinophilic esophagitis. • To evaluate the safety of Viaskin® Milk EPIT in subjects with milk-induced eosinophilic esophagitis. 	

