13.5 Analysis Populations

All the analysis populations will be identified and finalized in the SAP.

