13.5.1 Safety Population

The safety population will be comprised of all subjects who are randomized and received at least one dose of study drug. This population will be used to assess comparative safety information.

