#### **2.4.2 Randomization and replacement**

Approximately 22 eligible subjects to obtain 18 completed subjects will be randomized in a 3:1 ratio into two different treatment groups, (1) to receive EPIT with Viaskin® Milk (500 µg of milk proteins) or (2) placebo (16 subjects in the active Viaskin® Milk group and 6 subjects in the placebo group). Subjects who are withdrawn after beginning the treatment phase of the study will not be replaced. However, sufficient subjects will be included to ensure the minimum sample size.

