#### **3.1 Statistical design**

This is a randomized, double-blind, placebo-controlled clinical trial with Viaskin® Milk as Treatment 1 and placebo as Treatment 2. Primary and secondary efficacy objectives as well as the safety objectives are presented in Section 2.2.

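### The SAP's safety population adds a withdrawal-based clause for controls only; depending on how it is read, it drops placebo withdrawals or does almost nothing, and it should be deleted.

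*SAP*

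**What the plan says.** SAP 4.1 builds the safety population from two groups joined by *and*. The first is "all subjects who are randomized and received at least one dose of study treatment". The second is "all subjects in the control group who did not withdraw or were not withdrawn". Of the resulting set the SAP says: "This population will be used to assess comparative safety information".

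Protocol 13.5.1 has a single rule with no withdrawal condition: "all subjects who are randomized and received at least one dose of study drug". Protocol 13.5 hands the final definition to the SAP: "All the analysis populations will be identified and finalized in the SAP". The SAP wording would therefore govern.

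The documents do not settle whether placebo counts as study treatment. SAP 3.1 describes the trial "with Viaskin® Milk as Treatment 1 and placebo as Treatment 2", whereas the protocol synopsis has the field "NAME OF STUDY TREATMENT: Viaskin® Milk".

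The planned arms in SAP 2.4.2 are "16 subjects in the active Viaskin® Milk group and 6 subjects in the placebo group". SAP 3.2 gives 15 and 5.

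**The concern.** A safety comparison needs the same entry rule in both arms. Here controls alone have a clause that depends on something that happens after randomisation. Withdrawal is not neutral for safety: protocol 8.4.3.1 lists adverse events among the reasons for it, and SAP 2.2.6 makes discontinuation due to treatment-emergent events an endpoint. If the clause removes placebo subjects who withdrew, it can take out of the comparator the kind of event that stays counted in the active arm. With 5 or 6 placebo subjects, one such removal visibly changes the rates.

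The clause is also loosely worded. Taken literally, meeting either half is enough, so a control who left by choice but was not removed by the investigator could still qualify. Two programmers could derive different sets.

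**Working it through.** The plan states no figure on this point, so the check is to go through the readings and then size the one that does harm.

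**Step 1. What each reading does.**

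| Reading | Dosed placebo subject who withdraws in the double-blind period | Active subject who withdraws after one dose | Never-dosed control who does not withdraw |
|---|---|---|---|
| Protocol 13.5.1 | in | in | out |
| SAP, placebo counts as study treatment and *and* adds a second group | in | in | in |
| SAP, study treatment means active only | out | in | in |
| SAP, clause restricts controls | out | in | out |

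No SAP reading reproduces the protocol's rule. On the second row the only difference is the never-dosed control. Protocol 9.4 places randomisation and the first patch, applied on site by the investigator, at the same visit (Visit 4), so such a subject should be rare.

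**Step 2. Size on the excluding readings.**

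Inputs: placebo arm n = 6 (SAP 2.4.2) or 5 (SAP 3.2). Dropout d = 10% (SAP 3.2, protocol 13.2), or the rate implied by 22 randomised and 18 completed, (22 − 18)/22 = 18.2%. Assumption: both arms drop out at the same rate.

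- Share of the arm lost per exclusion: 1/6 = 16.7%; 1/5 = 20%.
- Expected withdrawals among 6: 6 × 0.10 = 0.6; 6 × 0.182 = 1.1.
- P(at least one withdrawal) = 1 − (1 − d)^n:

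| n | d = 10% | d = 18.2% |
|---|---|---|
| 6 | 1 − 0.9^6 = 46.9% | 1 − 0.818^6 = 70.0% |
| 5 | 1 − 0.9^5 = 41.0% | 1 − 0.818^5 = 63.3% |

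- P(at least two of 6) = 11.4% at 10% and 30.0% at 18.2%.

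These probabilities cover the whole period to which the dropout figure applies. On the active-only reading, only withdrawals before the first open-label active patch lead to exclusion, so the chance of an actual exclusion is lower if some of the dropout falls in the open-label year.

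**Step 3. What that does to a table row.** Suppose the withdrawals occur in the double-blind period and are due to treatment-emergent events. Under the protocol rule with 6 placebo subjects, one such withdrawal reads 1/6 (16.7%) and two read 2/6 (33.3%). On the excluding readings they read 0/5 and 0/4. The shells for Tables 18 to 20 do not name their population; I take it to be the safety population, given its stated purpose.

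**The case against.** The best defence is that the harmful reading is the less natural one. Apart from the synopsis field, usage mostly treats placebo as a treatment: SAP 3.1 numbers it as Treatment 2, SAP 2.3 describes a placebo treatment, and protocol 8.5.2 and 8.5.5.2, both headed as study treatment, cover active and placebo patches. On that usage every dosed placebo subject is already in through the first group, and a clause that adds people removes nobody. This stands, and it limits the weight of the point.

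A reader might go further and infer that the placebo row for adverse events leading to discontinuation in Tables 18 and 19A must be zero whatever happens. The documents do not support that. All subjects move to open-label active after Visit 10 (protocol 8.5.1, SAP 2.3). On the active-only reading, a placebo-randomised subject who stops after that has had a dose of study treatment and enters through the first group. The shells are not split by period, so if columns follow the randomised arm the event appears under placebo. The restricting reading names no period, so its reach into the open-label year is undefined. Stopping the patch and withdrawing from the study also need not coincide (protocol 8.4.3.1).

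Nor does it follow that any discontinuation in the active arm would look drug-caused. Relatedness is judged event by event (protocol 12.1). SAP 4.3 reports disposition on the ITT population and lists reasons for discontinuation by arm. SAP 4.5.1 lists all adverse events by subject with the action taken. A placebo withdrawal would be seen there.

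Finally, SAP 4.5 plans no formal safety analysis, although the Table 21 shell calls for Fisher's exact test on laboratory abnormalities. The damage would be to denominators and descriptive rates, and no efficacy analysis uses this set.

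None of this gives the clause a purpose. It either biases the comparison or does nothing useful.

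**Conclusion.** The safety population in SAP 4.1 is wrong as written: its entry rule differs by arm and departs from protocol 13.5.1 without explanation. The SAP cites protocol version 7.0 and the protocol in hand is 8.0, but a change of version would not justify an arm-specific rule.

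The size depends on the reading. Where placebo counts as study treatment and the clause only adds people, the effect is close to nil. Where study treatment is taken as active only, or the clause as restricting controls, double-blind placebo withdrawals are lost at 17 to 20% of the arm each. The chance that at least one of 6 withdraws is then about 47% to 70% over the whole dropout period, assuming equal dropout by arm. That would bias comparative adverse event and discontinuation rates, while the withdrawals themselves stayed visible in the disposition table and listings. It is a definition to correct before the safety tables are programmed, and it has no bearing on the efficacy result.

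**What to change.** Delete the control-group clause from SAP 4.1 and apply the protocol 13.5.1 rule to both arms: all randomised subjects who received at least one patch, active or placebo. Naming both patches removes the ambiguity in *study treatment*.

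SAP 4.1 gives a grouping rule for the ITT population but none for the safety population. Protocol 13.5.1 does not ask for grouping by treatment received. If that is added, the SAP should also say how placebo subjects are counted once they cross to open-label active at Visit 10.

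The cost is one SAP sentence, or two with the grouping rule. No data collection, sample size or efficacy analysis changes.

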## 4.2 Descriptive analyses

Standard descriptive statistics will be used to describe subjects' baseline characteristics and study endpoint measures overall and within each treatment group. Summary statistics such as means, standard deviations, medians, interquartile range and ranges for continuous variables (e.g., age, height, weight, and maximum esophageal eosinophil count) and frequency counts and percentages for categorical variables (e.g., race and ethnicity) will be generated. Medical histories will be summarized by system organ class and preferred term.

Demographic characteristics (*Table 1*), medical history (*Table 2*), vital signs at baseline (day 1), end of the double-blind treatment (visit 10), and end of the open-label treatment (visit 16) (*Table 3*), and both hematology and chemistry laboratory test results at baseline, end of the double-blind treatment, and end of the open-label treatment (*Table 4A* and *Table 4B*) will be summarized. Transformation (e.g., logarithmic transformation) of some of the continuous variables will be applied if needed.

## 4.3 Subject disposition

Subject disposition will be summarized for the ITT population. Subjects in each study population (ITT, PP, and Safety), subjects who received study medication, and subjects who completed and discontinued the double-blind period as well as the open-label period will be summarized (e.g., frequency counts and percentages) by treatment groups and overall (*Table 5*). The primary reason for discontinuation from the double-blind period and the open-label period will be listed by treatment groups.

## 4.4 Efficacy analyses

The methods for the primary and secondary efficacy analyses are described.

#### **4.4.1 Primary efficacy analyses**

Descriptive statistics for the maximum esophageal eosinophil count (the primary efficacy endpoint) on all specimens obtained on the biopsy at baseline (Day 1) and end of treatment (Visit 10) as well as the change from baseline to end of treatment will be presented by treatment groups and age groups (4-11 years old and 12-17 years old) (*Table 6*). The primary efficacy endpoint of the maximum esophageal eosinophil count will be analyzed using an analysis of covariance (ANCOVA) models with the treatment group (active versus placebo) and baseline patient's maximum esophageal eosinophil count. The least square means for the treatment groups, difference in least square means between the treatment groups, and a two-sided 95% CI for the difference between treatment groups will be presented (*Table 7*). Analysis of the primary endpoint in the logarithmic scale will be considered. Geometric mean and geometric mean ratio (anti-log of the parameter estimates) with 95% CIs will be reported when analyses are performed in the logarithmic scale of the primary endpoint.

#### **4.4.2 Secondary efficacy analyses**

Descriptive statistics for the secondary efficacy endpoints will be presented by treatment groups. The following secondary efficacy endpoints will be assessed:

##### **4.4.2.1 Total esophageal endoscopy score**

The total score for each subject will be calculated and summary statistics at baseline, end of the double-blind treatment, and end of the open-label treatment as well as the changes from baseline to end of the double-blind treatment and to end of the open-label treatment will be presented by treatment groups (*Table 8*). Hodges-Lehmann estimate with 95% CI for difference of median of the changes in esophageal endoscopy

scores between two treatment groups will be reported. The total score at the end of the double-blind treatment and at the end of the open-label treatment between two treatment groups will be analyzed separately using ANCOVA as described in Section 4.4.1. The least square means for the treatment groups, difference in least square means between the treatment groups, and a two-sided 95% CI for the difference between the treatment groups will be presented (*Table 9*).

#### **4.4.2.2 Eosinophilic esophagitis symptom and global assessment scores**

Summary statistics for individual eosinophilic esophagitis symptom score (Abdominal/Chest pain, Vomiting/Regurgitation, and Dysphagia) as well as investigator's eosinophilic esophagitis global assessment score at baseline, end of the double-blind treatment, and end of the open-label treatment as well as changes from baseline to end of the double-blind treatment and to end of the open-label treatment will be presented by treatment groups and overall (*Table 10*). The total EoE symptom score for each subject will be calculated and summary statistics at baseline, end of the double-blind treatment, and end of the open-label treatment, as well as the changes from baseline to end of the double-blind treatment and to end of the open-label treatment will be presented by treatment groups and overall. Improvement in symptom scores will be defined as a decrease in total eosinophilic esophagitis symptom score of two or more from baseline to end of the double-blind treatment and to end of the open-label treatment. Subjects will be categorized based on whether they improved their symptoms in two different ways. First, subjects who improved their symptom scores are considered as responders and subjects who did not improve their symptom scores are considered as non-responders. Second, subjects who improved their symptom scores will be categorized as poor improvement (<30%), good improvement (30-70%), and excellent improvement (>70%). RR or OR along with 95%

CI for the percentage of responders between two treatment groups will be presented. (*Table 11*).

In addition, frequency and severity EoE symptom scores measured by Pediatric Eosinophilic Esophagitis Symptoms Score (PEESS) will be examined. Summary statistics for the frequency and severity EoE symptom scores at baseline, end of the double-blind treatment, and end of the open-label treatment will be reported for each treatment group and overall. The changes in frequency and severity EoE symptom scores from baseline to end of the double-blind treatment and to end of the open-label treatment will be reported and Hodges-Lehmann estimates with 95% CIs for differences of medians of these changes between two treatment groups will be reported (*Table 12*).

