8.2 Discussion of Study Design

The current study is a pilot study powered to show statistical significance versus placebo. The design of this study is based on standard procedures used in clinic practice.

This study is also randomized and double-blinded with regard to treatment with Viaskin® Milk and matching placebo in order to prevent bias in treatment allocation and in the assessment of both safety and efficacy. The use of a placebo group in this trial is justified to obtain reliable scientific evidence for the evaluation of new medicinal products. The overall benefit to risk ratio for this trial is favorable. Subjects eligible to participate in this study must have a positive upper endoscopy with biopsy showing greater than or equal to 15 eosinophils/hpf when on milk containing diet, and that normalized (0-10 eosinophils/hpf) when milk was removed from the diet. The prospect of direct benefit is resolution of food allergy in EoE, which will be the first cure in the disease. The risk of the trial is due to the Viaskin® Milk EPIT patch, which resulted in non-serious adverse events in the phase 1 trial. The other risks are one research upper endoscopy with biopsies under sedation or general anesthesia, which the investigative team believes is a minor increase above minimal risk procedure when done by board certified gastroenterologist. The second risk is reoccurrence of EoE symptoms in placebo group or non-responders. Therefore, we have incorporated a period of 1 week to 2 month to milk re-exposure to minimize symptoms of EoE. The primary endpoint in this study will be assessed at the end of the treatment period, after up to 11 months of EPIT treatment. After the initial double-blind phase, all subjects will receive open-label active treatment for up to additional 11 months for collection of safety and efficacy data.

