9.3 Visit 3: Screening; Minimum 6 weeks after Removing Milk

Subjects will have a minimum of two standard of care upper endoscopies and biopsy to confirm milk induced EoE performed, after a minimum of 6 weeks under milk-free diet and while on proton pump inhibitor. Results of the standard of care endoscopy and biopsy will be obtained by review of medical records. Research procedures at this visit include EoE Quality of life measure, and collection of any AEs. Subjects' clinical care GI and Allergy physicians will determine the order of screening standard of care endoscopies.

The following assessments/procedures will be performed:

- Physical examination (including a complete skin examination).
- Vital signs (including heart rate, blood pressure, respiratory rate, and temperature).
- Eosinophilic Esophagitis Symptom Score (see Section 11.12)
- Eosinophilic Esophagitis (Age-specific) Quality of Life Measure (Appendix 2).
- Milk-free Diet
- Diet History
- Upper endoscopy and biopsies of the esophagus (see Section 11.8) with upper endoscopy score (Appendix 2)
- Record all AEs (volunteered or in response to an open question).
- Record of all concomitant medications.

9.4 Visit 4: Eligibility/Randomization Treatment Period; Day 1

Visit 4 corresponds to the first day of treatment.

The following assessments/procedures will be performed:

- Review Pathology reports of the upper endoscopy and biopsy. Confirm eligibility by chart review of clinical records/randomize subject.
- Physical examination (including a complete skin examination).
- Vital signs (including heart rate, blood pressure, respiratory rate, and temperature).
- Eosinophilic Esophagitis Symptom Score (see Section 11.12).
- Urine pregnancy test for female of childbearing potential.
- Milk-free Diet
- Dispense diary cards (instruct subject how to complete).
- Dispense the first treatment box of investigational product to the subject.
- The investigator will take one Viaskin® patch from the box, apply the first Viaskin® to the subject, and train the subject on the proper technique and timing for applying the other patches.
- The subject will remain either in the CHOP clinic exam room or in the waiting room for at least 3 hours under observation. Patients will regularly be assessed by study staff. Should a patient experience an adverse reaction, or emergency, the patch will immediately be removed and the site cleaned. Patient will then be treated per CHOP allergy clinic emergency procedures.

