13.6.4.2 Secondary Efficacy Variables

The following secondary efficacy endpoints will be assessed:

Esophageal Eosinophil Count

The mean Esophageal Eosinophil Count of all specimens obtained at the end of treatment as well as the change from baseline will be summarized by treatment group.

The null hypothesis that the mean Esophageal Eosinophil Count eliciting doses at the end of treatment are the same in each treatment group will be analyzed using ANCOVA model with treatment group, baseline patient's mean esophageal eosinophil count, and age group (4-11 years old versus 12-17 years old) as covariates. This null hypothesis will be tested against the alternative hypothesis that the results are different in each treatment group at the 0.05 significance level.

Esophageal Endoscopy Score

The total score for each subject will be calculated (for endoscopy) and summary statistics will be presented for each treatment group at baseline and the end of study. This will be based on each symptom being graded for severity as 0, 1, 2 or 3 (respectively none, mild, moderate and severe). The total scores at the end of treatment between two treatment groups will be examined using ANCOVA model with treatment group, baseline patient's total score, and age group (4-11 years old versus 12-17 years old) as covariates. The change from baseline to end of treatment will also be presented. The change in Esophageal endoscopy scores between two treatment groups will be examined using a two sample Student's t-test or Mann-Whitney test.

Eosinophilic Esophagitis Symptom Score

Improvement in symptom scores will be defined as a decrease in total symptom scores of two or more from baseline to end of treatment. Subjects will be categorized based on whether they improved their symptoms. Subjects who improved their symptom scores were considered as responders and patients who did not improve their symptom scores were considered as non-responders. The percentage of responders between the active treatment group and placebo group will be compared using Fisher's exact test. In addition, all of the summaries of severity of symptoms above will be repeated, split by responder/non-responder groups.

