# Baseline, Visit 10, and Visit 16 correspond to day 1, end of the double-blind treatment and end of the open-label treatment, respectively.

Values will be expressed as n, n missing, mean  $\pm$  SD, median (IQR), and range.

Table 4A. Summary Statistics for Laboratory Results (Hematology)

	All	Viaskin® milk	Placebo	
RBC count, MIL/ $\mu$ L				
Baseline #				
Visit 10 #				
Visit 16 #				
WBC count, Thou/ $\mu$ L				
Baseline				
Visit 10				
Visit 16				
Hemoglobin, g/dL				
Baseline				
Visit 10				
Visit 16				
Hematocrit, %				
Baseline				
Visit 10				
Visit 16				
Platelet count, Thou/ $\mu$ L				
Baseline				
Visit 10				
Visit 16				
Segmented neutrophils, cells/ $\mu$ L				
Baseline				
Visit 10				
Visit 16				
Lymphocytes, cells/ $\mu$ L				
Baseline				
Visit 10				
Visit 16				
Monocytes, cells/ $\mu$ L				
Baseline				
Visit 10				
Visit 16				

Eosinophils, cells/ $\mu$ L				
Baseline				
Visit 10				
Visit 16				
Basophils, cells/ $\mu$ L				
Baseline				
Visit 10				
Visit 16				

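### Symptom response requires a 2-point fall from what is most likely a milk-free baseline, so a child whose score holds steady on milk counts as a non-responder and the responder rows have little ability to show desensitization

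*SAP*

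**What the plan says.** SAP 4.4.2.2 defines the symptom responder by a fall in the total score: "Improvement in symptom scores will be defined as a decrease in total eosinophilic esophagitis symptom score of two or more from baseline". It applies this at the end of the double-blind period (Visit 10) and of the open-label period (Visit 16). All other children fall into one group: "subjects who did not improve their symptom scores are considered as non-responders". Those who improve are then graded by percent improvement. Protocol 13.6.4.2 gives the same rule, "Improvement in symptom scores will be defined as a decrease in total symptom scores of two or more from baseline to end of treatment", and compares responder percentages with Fisher's exact test. The SAP reports a relative risk or odds ratio with a 95% interval.

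The baseline visit for the symptom score is not named in SAP 4.4.2.2 or in Table 11. Where the SAP does identify baseline, it is Day 1:

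- for vital signs, in section 4.2: "vital signs at baseline (day 1), end of the double-blind treatment (visit 10), and end of the open-label treatment (visit 16"
- for the eosinophil count, in section 4.4.1: "all specimens obtained on the biopsy at baseline (Day 1) and end of treatment (Visit 10"
- for laboratory results, in the footnote to Table 4A: "Baseline, Visit 10, and Visit 16 correspond to day 1, end of the double-blind treatment and end of the open-label treatment, respectively"

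Protocol 9.4 identifies that day: "Visit 4 corresponds to the first day of treatment". The symptom score is collected then, and milk-free diet is listed among the visit's items. Protocol 8.2 describes the entry state as an esophageal count "that normalized (0-10 eosinophils/hpf) when milk was removed from the diet". Milk returns at Visit 9, and Visit 10 follows 1 week to 2 months later with the child on milk.

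**The concern.** The trial asks whether the patch keeps disease from returning when milk is given again. A child who starts off milk and is then challenged should show little or no change in symptoms if protected, and a rise if not. A rule that rewards only a fall suits a trial that starts in active disease. Used from a milk-free baseline, it does not separate the two outcomes the trial is designed to tell apart.

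This is the plan's dichotomous symptom endpoint, and SAP 2.2.3 makes the difference in improvement between arms part of secondary objective (a). The protocol also repeats the symptom severity summaries by responder group, so any misclassification carries into those tables.

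**Working it through.** The documents give no rate or power for this endpoint, so there is no stated figure to reproduce.

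**Inputs.** Total score 0 to 12, from three items scored 0 to 4 (protocol 11.12). Response if end-of-period score minus baseline is -2 or lower (SAP 4.4.2.2). Score collected before treatment at Visits 1, 2, 3 and 4 (protocol Table 3A); only Visit 2 is normally on milk. Arms of 16 and 6 (protocol 13.2). Fisher's exact test (protocol 13.6.4.2), taken as two-sided at 0.05.

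**Step 1: the rule applied to each course from a milk-free baseline b.**

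| Course on milk | Change | SAP 4.4.2.2 text | Table 11 footnote |
|---|---|---|---|
| Score unchanged, any b from 0 to 12 | 0 | non-responder | non-responder |
| Flare of 4 points, b from 0 to 8 | +4 | non-responder | responder |
| Best possible score of 0, b = 0 or 1 | 0 or -1 | non-responder | non-responder |
| Best possible score of 0, b = 2 or more | -2 or lower | responder | non-responder |

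The Table 11 footnote has the sign reversed: it calls a change of 2 or more (visit minus baseline) a response. Correcting it restores the text rule, and the problem in the first three rows remains. Percent improvement is undefined when b = 0. If neither arm has a responder, so are the relative risk and odds ratio.

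**Step 2: the ceiling on the responder rate.** Let s be the share of children with a Day 1 total of 2 or more. No arm's expected responder rate can exceed s. The documents do not give s, so a range is assumed.

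**Step 3: best-case power under the current rule.** Suppose every active child able to fall 2 points does so, and no placebo child does. With 0/6 on placebo, 8/16 active gives p = 0.051 and 9/16 gives p = 0.046, so 9 responders are needed. Power = P(X ≥ 9), X ~ Binomial(16, s):

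| s (assumed) | 20% | 30% | 40% | 50% | 60% |
|---|---|---|---|---|---|
| Power | 0.1% | 3% | 14% | 40% | 72% |

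**Step 4: power if response means no rise of 2 or more points.** Active success is assumed at 80%. Power is the sum, over all tables significant by Fisher's test, of the product of the two binomial probabilities:

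| Placebo success (assumed) | 10% | 20% | 30% | 40% | 50% |
|---|---|---|---|---|---|
| Power | 85% | 67% | 50% | 34% | 22% |

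The two tables rest on different assumptions and do not form a like-for-like comparison. Step 3 is an upper bound for each s.

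**The case against.** **The baseline visit is inferred.** The Day 1 statements cover vital signs, laboratory values and eosinophil counts, not symptoms. The label is also loose: section 4.4.1 places a biopsy at Day 1, yet no endoscopy takes place at Visit 4. If the on-milk Visit 2 score was meant, the rule is coherent. This stands as a limit on the claim. But Visits 1, 3 and 4 all lead to the same problem, and a plan that intends Visit 2 has to say so.

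**Histologic remission is not symptom remission.** Entry sets no symptom limit, protocol 6.2.1 says symptoms and biopsies do not always agree, and clinical care decides the order of the screening endoscopies. Some children may start at 2 or more. A reader might infer that the endpoint cannot show desensitization at all, or that both arms must be near 0%. The documents do not support that: at a share of 50% or 60% the best-case power is 40% or 72%. Even so, a fall from residual off-milk symptoms is not the same thing as protection under challenge.

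**Other symptom measures survive.** A reader might infer that a working patch would be reported as giving no symptom benefit. That does not follow. The SAP also reports total score and its change by arm, PEESS frequency and severity changes with intervals, and time to symptoms after milk. Any of these can show placebo children worsening while active children do not.

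**No power is claimed for this endpoint.** True. It is secondary, in a pilot sized on projected subject volume, and Fisher's test for it appears only in the protocol. The power figures show scale. The classification problem does not depend on them.

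**The alternative may not be powerful either.** Also true if few placebo children develop symptoms. Protocol 8.2 says the milk period was chosen to limit symptoms.

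**Conclusion.** The concern holds for the responder and percent-improvement rows. If the symptom baseline is Day 1 or any other milk-free visit, the rule puts a child whose score is unchanged on milk in the same class as a child who flares, and it excludes a child at 0 or 1 from ever responding. These rows then have little ability to show desensitization. How little depends on the undocumented share of children scoring 2 or more on Day 1: from almost none at 20% to a best case of 72% at 60%.

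The conclusion rests on reading baseline as milk-free, which is the likeliest reading but is not stated for this score. The primary analysis is unaffected. The case for changing the rule is that it should measure what the trial sets out to show; the gain in power is uncertain.

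**What to change.** In SAP 4.4.2.2, SAP Table 11 and protocol 13.6.4.2:

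1. Name Day 1 (Visit 4, milk-free) as the baseline for the symptom score.
2. Define the responder at Visit 10 as a child assessed after milk reintroduction whose total score is less than 2 points above Day 1. Use the same reference at Visit 16. This keeps the existing 2-point threshold.
3. State that a milk-free score carried forward cannot count as a response. SAP 3.3 applies last observation carried forward to secondary measures, so a child who leaves before reintroduction would otherwise become a responder without being challenged. Treat children not assessed on milk as non-responders or as missing, with a sensitivity analysis for the choice.
4. Report change from the on-milk Visit 2 score as supportive where it exists. Children who qualify on endoscopies from the preceding 12 months may not have one.
5. Rewrite the Table 11 footnote so that its sign agrees with the text.
6. Keep the percent-improvement bands, which the footnote attributes to an FDA request, as a descriptive row computed from the Visit 2 score where available.

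The cost is wording in two documents and one table shell, with no new data collection. The downside is that responder rates will no longer be comparable with those from trials that treat active disease.
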